6.1. Study Treatments Administered

6.1.1. Encorafenib

Encorafenib will be self-administered orally without regard to food. Encorafenib should be taken daily in the morning at approximately the same time (± 2 hours) every day. Patients should be directed to take encorafenib and binimetinib together as applicable. Patients will swallow the study intervention whole, and will not manipulate by, for example, opening or crushing, or chew the study intervention. If a patient vomits at any time after dosing, the dose should not be re-administered. Doses of encorafenib that are omitted for AEs or any other reason should not be made up during the day, or at the end of the dosing period. Additional information regarding encorafenib administration is provided in the IPM.

Encorafenib will begin on Cycle 1 Day 1 and will be self-administered continuously, except on study visit days (e.g., Day 1 of each cycle; see Table 3), and days when PK samples will be drawn (see Table 12 and Table 13), when the encorafenib dose will be administered at the study site under observation of the Investigator. Treatment may continue if the patient has not met any of the protocol-defined conditions for treatment withdrawal (see Section 6.7).

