6.1.2. Binimetinib

Binimetinib will be self-administered orally without regard to food. Binimetinib should be taken 12 ± 2 hours apart in the morning and in the evening at approximately the same times every day. Patients should be directed to take binimetinib and encorafenib together as applicable. Patients will swallow the study intervention whole, and will not manipulate by, for example, opening or crushing, or chew the study intervention. If a patient vomits at any time after dosing, the dose should not be re-administered, and the patient should take the next scheduled dose. Doses of binimetinib that are omitted for AEs or any other reason should not be made up during the day, or at the end of the dosing period. Additional information regarding binimetinib administration is provided in the IPM.

Binimetinib will begin on Cycle 1 Day 1 and will be self-administered continuously, except on study visit days (e.g., Day 1 of each cycle; see Table 3), and days when PK samples will be drawn (see Table 12 and Table 13), when the morning binimetinib dose will be administered at the study site under observation of the Investigator. Treatment may continue if the patient has not met any of the protocol-defined conditions for treatment withdrawal (see Section 6.7).

| Study Treatment Name | Encorafenib | Binimetinib |
|----------------------|-------------|-------------|
| Туре | Drug | Drug |

Table 6.Study Treatments

| Study Treatment Name | Encorafenib | Binimetinib |
|-------------------------|--|--|
| Dose Formulation | Capsule | Tablet |
| Unit Dose Strength | 75 mg | 15 mg |
| Dosage Levels | 450 mg QD | 45 mg BID |
| Route of Administration | Oral | Oral |
| Sourcing | Encorafenib will be provided centrally by the Sponsor or designee | Binimetinib will be provided centrally by the Sponsor or designee |
| Packaging and Labeling | Encorafenib will be provided in high-density polyethylene bottles. Each bottle will be labeled per local regulatory requirements. | Binimetinib will be provided in high-density polyethylene bottles. Each bottle will be labeled per local regulatory requirements. |
| Former Names or Aliases | LGX818 ONO-7702 W0090 | ARRAY-438162 MEK162 ONO-7703 W0074 |

Table 6.Study Treatments

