7.8. Pharmacokinetics

For patients enrolled under Protocol Versions 0 through 3, serial blood samples (~4 mL each) for plasma PK analysis of encorafenib, its metabolite (LHY746), and binimetinib will be collected as shown in Table 12.

For patients enrolled under Protocol Version 4 or later, blood samples (~4 mL each)for plasma concentration of encorafenib, its metabolite (LHY746), and binimetinib will be collected as shown in Table 13.

Complete instructions for sample processing, handling and shipment will be provided in the Laboratory Manual.

Study visits for PK sampling should be scheduled in the morning so that proper predose and postdose PK blood samples can be collected. On the PK visit days, the morning doses of encorafenib and binimetinib will be taken at the study site under observation by the Investigator or designee at approximately the same time, only after collecting the predose PK sample. Predose sampling information will include the date and exact time of the most recent previous dose of binimetinib and encorafenib (except Cycle 1 Day 1), including the dose amount taken. Postdose sampling information, only needed for days with postdose PK sampling (i.e., Cycle 1 Day 1 and Cycle 1 Day 15), will include the date and exact time of the morning dose, including the dose amount taken. Except for the Cycle 1 Day 1 PK samples, which have to be obtained on the scheduled day, other PK samples may be obtained ± 1 day from the scheduled date.

If vomiting occurs within 4 hours following study treatment administration on the day of PK sampling, no additional study treatment will be taken in an effort to replace the material that has been vomited and it is recommended that no more PK samples be taken after the emesis occurs. Any vomiting that occurs will be noted in the PK eCRF. Further doses will be administered with premedication with antiemetic medications and PK sampling will be performed after premedication with antiemetics.

In addition, exploratory analyses on remaining plasma samples may be performed using a validated or non-validated, semi-quantitative or qualitative liquid chromatography tandem mass spectrometry method, if deemed appropriate.

Table 12.Serial Pharmacokinetic Blood Sample Timing in Patients Enrolled under
Protocol Versions 0 through 3

| Study Visit | Timing of Sample |
|----------------|---|

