| Cycle 1 Day 1 | 0.5 hours (± 5 min) post dose 1.5 hours (± 5 min) post dose 3 hours (± 10 min) post dose 6 hours (± 20 min) post dose |
| Cycle 1 Day 15 | Predose (within 30 minutes prior to dose) 0.5 hours (± 5 min) post dose 1.5 hours (± 5 min) post dose 3 hours (± 10 min) post dose 6 hours (± 20 min) post dose |
| Cycle 2 Day 1 | • Predose (within 30 minutes prior to dose) |

Table 13.Pharmacokinetic Blood Sample Timing in Patients Enrolled under
Protocol Version 4 or later

| Study Visit | Timing of Sample |
|---------------|---|
| Cycle 1 Day 1 | • Predose (within 30 minutes prior to dose) |
| Cycle 2 Day 1 | • Predose (within 30 minutes prior to dose) |
| Cycle 3 Day 1 | • Predose (within 30 minutes prior to dose) |
| Cycle 4 Day 1 | • Predose (within 30 minutes prior to dose) |
| Cycle 5 Day 1 | • Predose (within 30 minutes prior to dose) |
| Cycle 6 Day 1 | • Predose (within 30 minutes prior to dose) |

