7.7.1. Plasma Concentrations of Encorafenib, LHY746, and Binimetinib

Plasma concentrations of encorafenib, its metabolite (LHY746), and binimetinib will be quantified at the time points indicated in Table 8:

Table 8. Pharmacokinetic Blood Sampling Times

Schedule ¹	Study Visit	Timing of Sample	Allowed Window
Serial	C1D1	0.5 hours postdose	± 5 min
		1.5 hours postdose	± 5 min
		3 hours postdose	± 10 min
		6 hours postdose	± 20 min
	C1D15	Predose	-30 min
		0.5 hours postdose	± 5 min
		1.5 hours postdose	± 5 min
		3 hours postdose	± 10 min
		6 hours postdose	± 20 min
		C2D1	Predose
Sparse	C1D1	Predose	-30 min
	C2D1	Predose	-30 min
	C3D1	Predose	-30 min
	C4D1	Predose	-30 min
	C5D1	Predose	-30 min
	C6D1	Predose	-30 min

¹ Serial blood sampling in participants enrolled under Protocol Version 0 through 3.0; sparse blood sampling for all participants enrolled from Protocol Version 4.0 onwards.

Protocol Amendment 4 implemented a change to the PK sampling schedule. All participants enrolled under the original protocol and up to and including Protocol Amendment 3 were subjected to serial PK blood sampling; however, all participants enrolled under Protocol Amendment 4 and later versions were subjected to sparse PK sampling assessments only (see

Table 8). Since there is only one common time point between the serial and sparse PK sampling schedules, separate PK TLFs will be presented for each sampling schedule.

All plasma concentration values for each participant in the safety set will be included in the bioanalytical plasma concentration listings, and participants will be identified as being in the PK set, as applicable. Individual concentration records will be flagged for the affected visit if any of the following occur:

- a. Participant had vomiting within 4 hours following study drug administration on the day of PK sampling (C1D1 and C1D15) or at any time over the preceding 24 hours.
- b. Plasma levels were not considered to be at steady-state (i.e. dosing was not performed for at least 4 consecutive days prior to C1D15 or C2D1).
- c. Subject received a higher or lower dose compared to planned treatment.
- d. PK sampling time was outside the allowed window or the elapsed time was not calculable.

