7.7.2. Plasma Pharmacokinetic Parameters for Encorafenib, LHY746, and Binimetinib

PK parameters for participants in the PK set will be determined for encorafenib, its metabolite (LHY746), and binimetinib, when possible and appropriate. Only participants assigned to the serial PK blood sampling schedule will be included in the PK parameter assessment.

The individual plasma concentration-time data for each analyte will be evaluated with noncompartmental analysis (NCA) using Phoenix WinNonlin®, Version 8.0 or higher. Actual blood collection times and doses will be used for PK calculations. If actual times are not recorded/available, nominal times will be used. All BLQ values before the observed maximum plasma concentration (C_{max}) will be set to 0; all BLQ values after C_{max} or embedded between two measurable values will be considered as missing.

The PK parameters that will be calculated for encorafenib, its metabolite (LHY746), and binimetinib on C1D1 and C1D15 are defined in Table 9.

The AUC parameters will be calculated according to the linear-up log-down trapezoidal rule. Additional PK parameters may be calculated at the discretion of the pharmacokineticist.

All PK parameter values will be presented in data listings by analyte, cycle and study day. Each parameter will be summarized in tables by line of therapy (treatment naive, previously treated, and overall), analyte, cycle and study day using the following descriptive statistics: N, n, arithmetic mean, standard deviation, CV, geometric mean, geometric CV, minimum, median and maximum. Descriptive statistics for in-text summary tables will include geometric mean with geometric CV for AUC, C_{max} , and RAUC. For T_{max} values, median, minimum and maximum will be presented. Pharmacokinetic parameters will be excluded from the calculation of summary statistics if any of the above flags [a-c] apply.

Table 9. Definitions of Pharmacokinetic Parameters

PK Parameter	Definition
AUC_{0-6}	Area under the plasma concentration-time curve from zero to 6 hours
AUC_{last}	Area under the plasma concentration-time curve from zero to the last measurable time point
AUC_{tau}	Area under the plasma concentration-time curve over a dosing interval at steady-state (C1D15 only) To estimate AUC_{tau} , the concentration measured at predose on C1D15 will be imputed as the concentration at the end of the dosing interval (i.e., 12 or 24 hours, as appropriate) assuming steady-state has been attained

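### No PK exclusion rule uses the time since the previous dose, so a mistimed predose sample can enter the trough summaries and the C1D15 AUCtau

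*Protocol*

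**What the plan says.** **Dosing times.** Protocol 6.1.2 says "Binimetinib should be taken 12 ± 2 hours apart in the morning and in the evening". Protocol 6.1.1 says "Encorafenib should be taken daily in the morning at approximately the same time (± 2 hours) every day". On visit days the morning doses are held and taken at the site.

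**Data collected.** Protocol 7.8 says "Predose sampling information will include the date and exact time of the most recent previous dose of binimetinib and encorafenib", with Cycle 1 Day 1 excepted.

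**Sampling window.** Protocol Tables 12 and 13 and SAP Table 8 give one window for a predose sample: the 30 minutes before the coming dose.

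**Exclusion flags, SAP 7.7.1.**
- Flag a concerns vomiting.
- Flag b is failure to reach steady state, explained as "dosing was not performed for at least 4 consecutive days prior to C1D15 or C2D1".
- Flag c is "Subject received a higher or lower dose compared to planned treatment".
- Flag d is "PK sampling time was outside the allowed window or the elapsed time was not calculable".

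Concentration summaries, troughs included, drop values with any of flags a to d. PK parameters (SAP 7.7.2) are dropped for flags a to c only.

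**AUCtau, SAP Table 9.** At steady state, "the concentration measured at predose on C1D15 will be imputed as the concentration at the end of the dosing interval", that is 12 or 24 h.

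**The concern.** A predose concentration is a trough only if it is drawn about one dosing interval after the previous dose: 12 h for binimetinib, 24 h for encorafenib and its metabolite LHY746. Closeness to the next dose does not establish that. The protocol constrains the quantity that matters and records it, but the analysis plan does not test it.

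Three exploratory outputs depend on it.

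- Trough summaries and trough-by-visit plots, for both sampling schedules. For patients enrolled under Version 4 or later, who have predose samples only, these are the only PK summary that does not come from a model.
- Ctrough and AUCtau in the serial-sampling patients (Versions 0 to 3).
- The Welch comparison of AUCtau by line of therapy in SAP 7.7.5, in the same serial-sampling patients.

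**Working it through.** The plan states no figure on this point to reproduce. The check is first textual, then an illustration of size.

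**1. Take one sample through the flags.** Suppose the evening binimetinib dose was taken 15 h before a C1D15 sample, and the sample was drawn 10 minutes before the clinic dose.
- Flag a: no vomiting, passes.
- Flag b: counts days of dosing, not hours, passes. It names only C1D15 and C2D1, so it does not reach the Cycle 3 to 6 troughs at all.
- Flag c: concerns the amount of the dose, not its time, passes.
- Flag d: 10 minutes is inside the window. The second limb catches a time that cannot be calculated, not one that is out of range, so the sample passes however elapsed time is read.

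The value enters the trough summary, and Table 9 places it at 12 h. Using actual collection times (SAP 7.7.2) does not help, because the end-of-interval point is assigned to the nominal time. Flag d is not applied to parameters, so for Ctrough and AUCtau even a breach of the 30-minute window excludes nothing.

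**2. Size of the trough error.** Half-lives T are not in the documents; 3, 5 and 9 h are assumed for illustration. With mono-exponential decay, reading ÷ true trough = 2^(−s/T), where s is the hours late.

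| | T = 3 h | T = 5 h | T = 9 h |
|---|---|---|---|
| 3 h late | 0.50 | 0.66 | 0.79 |
| 3 h early | 2.00 | 1.52 | 1.26 |

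**3. Size of the AUCtau error from the end value alone.** The last segment by the log-trapezoid rule is (C1 − C2)·Δt ÷ ln(C1/C2). For binimetinib with T = 3 h and C at 6 h set to 1:
- value at 12 h = 0.25, segment = 0.75 × 6 ÷ ln 4 = 3.246
- value at 15 h placed at 12 h = 0.125, segment = 0.875 × 6 ÷ ln 8 = 2.525
- change = 2.525 ÷ 3.246 − 1 = −22.2%

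That is the tail, not AUCtau. The tail's share of AUCtau comes from a one-compartment oral model at steady state (ka 1.5/h, assumed) on the C1D15 sampling times. Whole change = share × tail change:

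| 3 h late | T (h) | Tail share | Tail change | Whole AUCtau |
|---|---|---|---|---|
| Binimetinib | 3 | 24.2% | −22.2% | −5.4% |
| | 5 | 33.9% | −15.9% | −5.4% |
| | 9 | 41.0% | −9.9% | −4.1% |
| Encorafenib | 3 | 29.9% | −13.6% | −4.1% |
| | 5 | 46.3% | −11.7% | −5.4% |
| | 9 | 59.6% | −8.4% | −5.0% |

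For 3 h early the tail changes are +33.3%, +20.5%, +11.5% (binimetinib) and +18.1%, +14.4%, +9.6% (encorafenib). With the same shares, whole AUCtau rises by about 5% to 8%.

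**4. What the dosing rule allows.** Binimetinib: 12 ± 2 h gives 10 to 14 h. Encorafenib: two doses each within 2 h of the same clock time can be 24 − 4 = 20 h to 24 + 4 = 28 h apart. A sample may precede the dose by up to 0.5 h, so compliant samples fall 9.5 to 14 h after binimetinib and 19.5 to 28 h after encorafenib.

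**The case against.** The strongest reply is that little depends on this. PK is an exploratory objective, the affected outputs are mostly descriptive, and the line-of-therapy p-values are unadjusted. That stands, and it limits the weight of the point.

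Four stronger readings are tempting, and the documents do not support them.

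- *Troughs and AUCtau will be biased low.* This assumes that clinic doses run later than home doses. No passage says so. Protocol 7.8 asks for morning PK visits so that proper samples can be taken, and error in either direction is possible.
- *Previous-dose timing is never checked.* Protocol 6.4 has departures from the prescribed regimen recorded in source and the eCRF, and SAP 7.3 tabulates significant deviations under a separate document. The gap is narrower: no PK exclusion flag uses the time.
- *AUCtau is wrong by up to 22%.* That is the imputed tail only. A mistimed previous dose also changes the residual carried into the 0 to 6 h profile. With that included, the same model gives falls of about 9% to 12% (binimetinib) and 4% to 8% (encorafenib), but that part is actual exposure on the day, not an effect of placing the end value.
- *Efficacy or exposure-response conclusions are at risk.* The response-rate tests use none of these data. Exposure-response work uses population-model exposures under a separate plan (Protocol 8.4.4).

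Two further limits apply. A missed dose, as opposed to a mistimed one, may be caught by flag b or c. The line-of-therapy comparison is biased only if mistiming differs between the groups; otherwise the effect is added noise.

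**Conclusion.** The gap is real on the text: mistimed predose values can pass every rule in SAP 7.7.1 and 7.7.2, although the information to detect them is collected. How many such samples exist cannot be known from the documents.

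The trough error is the main issue: about 50% to 79% of the true value for a sample 3 h late, or 126% to 200% for one 3 h early, if half-lives are 3 to 9 h. The end-value effect on whole AUCtau is modest, about 4% to 5% low for a sample 3 h late, and rests further on the one-compartment model with ka 1.5/h. This is a worthwhile clarification of an exploratory analysis. It does not bear on the primary or secondary endpoints.

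**What to change.** - **Add flag e to SAP 7.7.1:** a predose sample after C1D1 whose recorded time since the previous dose is missing, or falls outside a window fixed in advance. Derive the window from the protocol's own dosing rule and allow for the 30-minute draw: for example 9.5 to 14 h for binimetinib, and 19.5 to 28 h, or a tighter limit set by the sponsor, for encorafenib and LHY746. The wide encorafenib window would still admit a 27 h sample, since the dosing rule can allow it. That is the argument for considering a tighter analysis limit.
- **Exempt C1D1.** There is no previous dose, and a missing-time rule would otherwise delete every C1D1 predose value from the Version 4+ schedule.
- **Exclude flagged values** from the trough summaries and plots.
- **Amend SAP 7.7.2** so that flag e, and flag d for the predose sample, also apply to Ctrough and to the end-of-interval value for AUCtau.

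Dosing, visits and sampling do not change, and the data are already collected. The cost is edits to two SAP sections and the loss of some trough and AUCtau values. Presenting the summaries with and without flagged values would show how much the exclusion matters.

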6.2. Preparation/Handling/Storage/Accountability

The Investigator or designee must confirm appropriate temperature conditions have been maintained during transit for all study treatment received and any discrepancies are reported and resolved before use of the study treatment.

Only patients enrolled in the study may receive study treatment and only authorized site staff may supply or administer study treatment. All study treatment must be stored in a secure, environmentally controlled, and monitored (manual or automated) area in accordance with the labeled storage conditions with access limited to the Investigator and authorized site staff.

The Investigator (or designee), is responsible for study drug accountability, reconciliation, and record maintenance (i.e., receipt, reconciliation, and final disposition records). Inventory and accountability records must be maintained and readily available for inspection by the study monitor and are open to inspection at any time by applicable regulatory authorities. The Investigator or designee must maintain records that document:

- Delivery of study drugs to the site.
- Inventory of study drugs at the site.
- Patient use of study drugs including capsule/tablet counts from each supply dispensed.
- Return of study drugs to the Investigator or designee by the patient.

The study treatment must be used only in accordance with the protocol. The Investigator will also maintain records adequately documenting that the patient was provided with the specified study drugs. These records should include dates, quantities, and any available batch or serial numbers or unique code numbers assigned to the study drugs and study patients.

Completed accountability records will be archived by the site. The Investigator or designee will be expected to collect and retain all used, unused, and partially used containers of study drugs until verified by the study monitor (unless otherwise agreed to by the Sponsor). At the conclusion of the study, the Investigator or designee will oversee shipment of any remaining study drug back to the Sponsor or designee, or destruction of study drug according to institutional standard operating procedures.

Detailed information on study drug preparation, handling, storage and accountability will be provided in the IPM.

6.3. Randomization and Blinding

6.3.1. Randomization and Blinding

No randomization or blinding mechanisms will be used in this open-label study; however, the study treatment will be dispensed using an IWRS. The site will contact the IWRS to enroll the patient and to obtain the study drugs. All subsequent cycles will follow this process. The IWRS will also be used to order study drug supplies and document when patients are discontinued from treatment. Full details will be provided in the Study Manual.

6.3.2. Patient Numbering

Each patient is identified in the study by a Patient Number (Patient No.), that is assigned when the patient enters the screening period and is retained as the primary identifier for the patient throughout his/her entire participation in the study. The Patient No. consists of the 4 digits Center Number (as assigned by the Sponsor or designee to the investigative site) with a sequential patient number suffixed to it (the last 4 digits of the Patient ID), so that each patient is numbered uniquely across the entire database. Upon signing the informed consent form, the patient is assigned to the next sequential Patient No. available to each Investigator through IWRS. Once assigned, the Patient No. must not be reused for any other patient and the Patient fails to be enrolled or start treatment for any reason, the reason will be entered into the eCRF. Refer to Section 5.4 for further information on data collected for screen failures. The IWRS must be notified within 2 days that a patient did not initiate study drug dosing.

